## **8.2 Lost to Follow Up**

A participant will be considered lost to follow-up if he or she fails to return for 3 scheduled visits and is unable to be contacted by the study site staff.

The following actions must be taken if a participant fails to return to the clinic for a required study visit:

- The site will attempt to contact the participant and reschedule the missed visit and counsel the participant on the importance of maintaining the assigned visit schedule and ascertain if the participant wishes to and/or should continue in the study. If treatment cannot be resumed within 12 weeks from last administration, patient will go off treatment.
- Before a participant is deemed lost to follow-up, the investigator or designee will make every effort to regain contact with the participant (where possible, 3 telephone calls and, if necessary, a certified letter to the participant's last known mailing address or local equivalent methods). These contact attempts should be documented in the participant's medical record or study file.
- Should the participant continue to be unreachable, he or she will be considered to have withdrawn from the study with a primary reason of lost to follow-up.

## **9. Correlative/Special Studies**

Correlative studies analyzing blood, archival tumor tissue, and new tumor biopsies will run concurrently with the study. We will investigate biomarkers to prognosticate response and immune related side effects. All findings will be correlated with patient outcomes.

We will assess gene expression and immune cell infiltrates at baseline. In case of severe autoimmune disorders after initiation of KN046 treatment, tissue-directed biopsies and blood will

be drawn for TCR sequencing and to assess circulating levels of cytokines. The primary hypothesis will be that treatment will reduce systemic levels of cytokines associated with a suppressive myeloid environment in patients who develop irAEs. To that end, we will quantify pre and on treatment levels of the following cytokines: IL-8, IL-6, and IL-1 all of which have been associated with a non-permissive tumor microenvironment. As a secondary hypothesis, we will test whether levels of pro-inflammatory cytokines are increased in a compensatory manner – those studies will focus on IFN- $\gamma$ , IL-12 and IL-2.

### **9.1. Laboratory Correlative Studies**

Correlative laboratory studies will be collected, sent, and stored to the PI's laboratory, located on [name].

#### **9.1.1 Laboratory Correlative Study**

We will obtain baseline neutrophil-to-lymphocyte ratio (NLR) and absolute lymphocyte counts (ALC) since ALC >2000 (26) and NLR <3 (27) have been shown to be correlated with an increased risk of irAEs. Levels of multiple cytokines and chemokines reflecting inflammatory immune responses (IL-6, IL-10, IFN- $\gamma$ , CXCL10/11, TNF $\alpha$ , CCL2, CCL5, etc.) will be measured using human cytokine array (HD71; Eve Technologies). A CYTOX score was identified in melanoma patients, which predicts early risk of severe irAEs (28). We will use these laboratory results to validate CYTOX as a biomarker for toxicity in patients on immune checkpoint blockade.

Circulating tumor DNA will be sequentially assessed at baseline, at time of best response and at tumor progression. Autoantibodies against Acetylcholine Receptor, striated muscle (anti-SM) and muscle-specific kinase (MUSK) will be assessed at baseline. Patients with elevated autoantibodies at baseline will be excluded. Blood samples for TCR sequencing will be collected at baseline and if irAE occurs.

##### **9.1.1.1 Collection of Specimen(s)**

Serial blood samples will be collected for serum and peripheral blood mononuclear cells (PBMC) at baseline and during treatment. Timepoints will be at baseline, after 2 cycles, and at occurrence of irAE (if any).

##### **9.1.1.2 Handling of Specimen(s)**

Whole blood samples will be stored in -80 C within 16 hours to preserve nucleic acid quality. Formalin-fixed paraffin-embedded (FFPE) unstained sections will be stored in +4 C and FFPE blocks will be stored at room temperature.

### **9.2. Special Studies**

#### **9.2.1 Special Correlative Studies**

We hypothesize that additional mutations may appear after chemotherapy that could potentially lead to PD-L1 upregulation in thymic carcinomas and therefore induce sensitivity to PD-1 antibody therapy. Thus we plan to explore whether specific genetic mutations and the number of mutations are associated with PD-L1 expression in thymic carcinomas and patients' response to KN046 therapy (targeting CTLA-4 and PD-L1). Attempts will be made to obtain tumor material before enrolling onto this study. Samples (fresh or FFPE samples) collected post chemotherapy and their normal blood pairs as well as 10 fresh or archived FFPE tumor materials derived from the same patients before systemic chemotherapy will be sequenced using NEXTGEN technology focusing on all the identified recurrent mutations in thymic carcinomas [33; 38], published cancer driver genes

[39] and COSMIC cancer gene census (<http://cancer.sanger.ac.uk/cosmic/census>). Comparative sequencing analysis of the tumor/blood pairs allows us to identify specific somatic mutations and the number of somatic mutations in a given tumor. Moreover, comparative analysis of tumor samples from the same patient before and after systemic treatment can uncover whether the tumor may acquire additional mutations after chemotherapy. The data will be employed to evaluate the correlation between the type/number of mutations and PD-L1 expression in the tumors and patients' response to PD-1 antibody therapy.

#### **9.2.1.1 Assessment**

For archival tumor specimens, gene expression profiling (GEP) by Nanostring (12), RNAseq and Whole Exome Sequencing (WES) will be performed and results will be correlated with clinical outcome and response to therapy. We will obtain normal peripheral blood as a control for WES. Tumor specimens will also be evaluated for tumor-infiltrating lymphocyte (TIL) infiltration. The main immune cell subsets will be quantified by immunohistochemical analysis for markers of T cells (CD3, CD4, CD8, FoxP30), DC (CD11c) and macrophages (CD68), and for expression of PD-L1.

#### **9.2.1.2 Method of Assessment**

Whenever feasible, fresh tissue will be obtained to establish organoids(29, 30). If sufficient tumor material is available, attempts will also be made to develop patient-derived xenograft (PDX) models. Both organoids and PDX tumors will be characterized with several immunohistochemistry markers and by sequencing as described above. Organoids will be subjected to in vitro drug testing using a robotic platform that is available in our cancer center through the Weill Cornell Medicine Engleander Institute for Precision Medicine. PDX models will be subjected to in vivo drug testing. TCR sequencing will be performed on tumor, sequential blood samples and non-lesional/lesional tissue biopsies in patients who develop autoimmune disorders, using the Adaptive platform (12).

#### **9.2.1.3 Timing of Assessment**

On-treatment biopsies would be obtained at time of irAE development if it occurs.

### **10. Measurement of Effect**

#### **10.1 Response Criteria**

RECIST v1.1 will be applied by the site as the primary measure of tumor assessment and response and as the basis for protocol guidelines related to disease status (e.g., discontinuation of study treatment).

Radiological scans of all suspected sites of disease will be performed utilizing the same method and technique throughout the study. Target lesions should demonstrate the patient's baseline tumor burden and will be selected based on size (i.e., lesions with the longest diameter), and suitability for accurate repeat assessment.

The following should be performed:

- PET-CT scans are required for all patients at Screening, at the time of best response, and as clinically indicated
- Chest, abdomen, and pelvis CT (Chest CT and Abdomen/Pelvis MRI acceptable) are required for all patients every 2 cycles for the first year and then every 4 cycles for the second year.

Additional imaging evaluations may be performed at any time if there is symptomatic evidence suggesting the possibility of disease progression based on clinical symptoms or physical examination.

### **10.2 Duration of response**

Among subjects with a confirmed response (PR or CR) per RECIST 1.1, duration of response (DOR) is defined as the time from first documented response (PR or CR) to the date of first documented disease progression or death due to underlying cancer. DOR will be listed by subject and described using Kaplan-Meier curves and relevant statistics if appropriate.

### **10.3 Progression-Free Survival**

PFS is defined as the duration of time from start of treatment to time of progression.

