**Table 2-1      Subject disposition for Trial KN046-AUS-001 (Safety Population)**

	0.3 mg/kg Q2W (N = 1)	1.0 mg/kg Q2W (N = 3)	3.0 mg/kg Q2W (N = 17)	5.0 mg/kg Q2W (N = 30)	10.0 mg/kg Q2W (N = 3)	Total (N = 54)
Subjects enrolled	1 (100%)	3 (100%)	17 (100%)	30 (100%)	3 (100%)	54 (100%)
Subjects dosed	1 (100%)	3 (100%)	17 (100%)	30 (100%)	3 (100%)	54 (100%)
Treatment ongoing at data cut-off	0	0	1 (5.9%)	7 (23.3%)	0	8 (14.8%)
Treatment termination	1 (100%)	3 (100%)	15 (88.2%)	22 (73.3%)	3 (100%)	44 (81.5%)
Confirmed disease progression	1 (100%)	2 (66.7%)	10 (58.8%)	12 (40.0%)	1 (33.3%)	26 (48.1%)
Intercurrent illness that prevents further administration of treatment	0	0	0	1 (3.3%)	0	1 (1.9%)
Unacceptable adverse experiences	0	1 (33.3%)	0	5 (16.7%)	1 (33.3%)	7 (13.0%)
Subject withdraws consent	0	0	1 (5.9%)	1 (3.3%)	1 (33.3%)	3 (5.6%)
If in the opinion of the Investigator, a change or discontinuation of therapy would be in the best interest of the subject	0	0	3 (17.6%)	2 (6.7%)	0	5 (9.3%)
Death	0	0	1 (5.9%)	0	0	1 (1.9%)
Other	0	0	0	1 (3.3%)	0	1 (1.9%)

Note: 1. Percentages are based on the number of subjects of each dose level in the evaluable analysis set.

Program: t\_tte.sas

Executed: 20FEB2020 23:24

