**Table 2-2 Safety summary for Trial KN046-CHN-001 (Safety Population)**

	0.3 mg/kg Q2W (N = 1)	1.0 mg/kg Q2W (N = 3)	3.0 mg/kg Q2W (N = 17)	5.0 mg/kg Q2W (N = 30)	10 mg/kg Q2W (N = 3)	Total (N = 54)
Number of TEAE	5	35	153	271	34	498
Subjects with at least 1 TEAE	1 (100%)	3 (100%)	17 (100%)	28 (93.3%)	3 (100%)	52 (96.3%)
Related to KN046	1 (100%)	2 (66.7%)	13 (76.5%)	22 (73.3%)	3 (100%)	41 (75.9%)
Subjects with at least 1 CTCAE Grade $\geq$ 3 TEAE	0	2 (66.7%)	11 (64.7%)	19 (63.3%)	3 (100%)	35 (64.8%)
Related to KN046	0	2 (66.7%)	4 (23.5%)	11 (36.7%)	3 (100%)	20 (37.0%)
Subjects with at least 1 DLT Event	0	0	0	1 (3.3%)	2 (66.7%)	3 (5.6%)
Subjects with at least 1 irAE	0	2 (66.7%)	9 (52.9%)	12 (40.0%)	3 (100%)	26 (48.1%)
Subjects with at least 1 CTCAE Grade $\geq$ 3 irAE	0	1 (33.3%)	3 (17.6%)	6 (20.0%)	3 (100%)	13 (24.1%)
Subjects with at least 1 Infusion Reaction	0	1 (33.3%)	3 (17.6%)	4 (13.3%)	0	8 (14.8%)
Subjects with at least 1 CTCAE Grade $\geq$ 3 Infusion Reaction	0	0	0	0	0	0
Subjects with at least 1 Treatment-emergent SAE	0	1 (33.3%)	9 (52.9%)	14 (46.7%)	2 (66.7%)	26 (48.1%)
Related to KN046	0	1 (33.3%)	4 (23.5%)	7 (23.3%)	2 (66.7%)	14 (25.9%)
Subjects with at least 1 CTCAE Grade $\geq$ 3 Treatment-emergent SAE	0	1 (33.3%)	7 (41.2%)	12 (40.0%)	1 (33.3%)	21 (38.9%)
Related to KN046	0	0	3 (17.6%)	6 (20.0%)	1 (33.3%)	10 (18.5%)
Subjects with at least 1 TEAE Leading to Drug Withdrawn	0	1 (33.3%)	1 (5.9%)	7 (23.3%)	1 (33.3%)	10 (18.5%)
Related to KN046	0	1 (33.3%)	1 (5.9%)	4 (13.3%)	1 (33.3%)	7 (13.0%)
Subjects with TEAE Leading to Death	0	0	0	2 (6.7%)	0	2 (3.7%)
Related to KN046	0	0	0	0	0	0

Note: 1. Percentages are based on the number of subjects of each dose level in the safety analysis set. 2. MedDRA 22.0 3. CTCAE 4.03

Program: t\_ae\_pt.sas

Executed: 20FEB2020 23:21

**Table 2-3** *Treatment related TEAEs (TRAEs) for Trial KN046-AUS-001 (Safety Population)*

Preferred Term	0.3 mg/kg Q2W (N = 1)		1.0 mg/kg Q2W (N = 3)		3.0 mg/kg Q2W (N = 17)		5.0 mg/kg Q2W (N = 30)		10.0 mg/kg Q2W (N = 3)		Total (N = 54)	
	All grades	Grade≥3	All grades	Grade≥3	All grades	Grade≥3	All grades	Grade≥3	All grades	Grade≥3	All grades	Grade≥3
Subjects with at least 1 KN046 related TEAE	1 (100%)	0	2 (66.7%)	2 (66.7%)	13 (76.5%)	4 (23.5%)	22 (73.3%)	11 (36.7%)	3 (100%)	3 (100%)	41 (75.9%)	20 (37.0%)
Arthralgia	0	0	1 (33.3%)	0	4 (23.5%)	0	4 (13.3%)	1 (3.3%)	0	0	9 (16.7%)	1 (1.9%)
Fatigue	0	0	0	0	0	0	7 (23.3%)	0	1 (33.3%)	1 (33.3%)	8 (14.8%)	1 (1.9%)

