(19.3%), fatigue in 15 subjects (17.0%), infusion related reaction in 15 subjects (17.0%), aspartate aminotransferase (AST) increased in 12 subjects (13.6%), pyrexia in 11 subjects (12.5%) and arthralgia in 9 subjects (10.2%). 9 of the 88 subjects (10.2%) experienced at least one  $\geq$ Grade 3 TRAEs. These included event terms of infusion related reaction (4 subjects; 4.5%), AST increased (3 subjects; 3.4%), rash (2 subjects; 2.3%), ALT increased (1 subject; 1.1%), anemia (1 subject; 1.1%), hyponatremia (1 subject; 1.1%) and transaminase increase (1 subject; 1.1%). No Grade 5 TRAEs were observed. Four (4.5%) subjects experienced treatment-related SAE. The event terms of the treatment-related serious TEAEs included infusion related reaction (2 subjects; 2.3%), ALT increased (1 subject; 1.1%), AST increased (1 subject; 1.1%), pneumonitis (1 subject; 1.1%), rash (1 subject; 1.1%) and transaminases increased (1 subject; 1.1%). 40 (45.5%) subjects had experienced irAEs, Four (4.5%) were grade 3. The event terms of these irAEs include rash (2 subjects; 2.3%), ALT increased (1 subject; 1.1%), AST increased (1 subject; 1.1%), pneumonitis (1 subject; 1.1%) and transaminase increased (1 subject; 1.1%). None irAE led to death. Similar to the results of the KN046-AUS-001 trial, neither the treatment-related TEAEs nor the irAEs in the dose escalation study of the KN046-CHN-001 trial were found to occur in a dose-dependent manner.

Overall, the TEAE profile was similar across different dose cohorts and the incidences of TEAEs by TEAE category did not increase with increasing dose.

**Table 2-7** *Subject disposition for Trial KN046-CHN-001 (Safety Population)*

Subject disposition	1.0 mg/kg Q2W (n = 1)	3.0 mg/kg Q2W (n = 30)	5.0 mg/kg Q2W (n = 45)	5.0 mg/kg Q3W (n = 6)	300 mg (n = 6)	Total (N = 88)
Subjects remaining on treatment (%)	0	8 (26.7%)	22 (48.9%)	2 (33.3%)	1 (16.7%)	33 (37.5%)
Discontinued, n (%)	1 (100%)	22 (73.3%)	23 (51.1%)	4 (66.7%)	5 (83.3%)	55 (62.5%)
Disease progression	1 (100%)	17 (56.7%)	14 (31.1%)	2 (33.3%)	2 (33.3%)	36 (40.9%)
Adverse events	0	2 (6.7%)	3 (6.7%)	0	0	5 (5.7%)
Death	0	0	0	1 (16.7%) 	2 (33.3%) 	3 (3.4%)
Lost to follow-up	0	1 (3.3%)	1 (2.2%)	0	0	2 (2.3%)
Other reasons 	0	2 (6.7%)	5 (11.1%)	1 (16.7%)	1 (16.7%)	9 (10.2%)

1 Death from disease progression

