2 One subject died from Acute Respiratory Distress Syndrome; For another subjects, the investigator was not be able to determine the reason for the death

3 Other reasons including eight patients discontinued due to clinical deterioration, one patient discontinued due to investigator determined no longer clinical benefit.

Source: Table 1 Dated 20200213

**Table 2-8** *Safety summary for Trial KN046-CHN-001 (Safety Population)*

CTCAE version 5.0	1.0 mg/kg Q2W (N = 1)	3.0 mg/kg Q2W (N = 30)	5.0 mg/kg Q2W (N = 45)	5.0 mg/kg Q3W (N = 6)	300 mg Q3W (N = 6)	Total (N = 88)
Subjects with at least 1 TEAE	1 (100%)	30 (100%)	44 (97.8%)	6 (100%)	6 (100%)	87 (98.9%)
Related to KN046	1 (100%)	27 (90.0%)	36 (80.0%)	6 (100%)	4 (66.7%)	74 (84.1%)
Subjects with at least 1 CTCAE Grade ≥ 3 TEAE	1 (100%)	14 (46.7%)	9 (20.0%)	2 (33.3%)	4 (66.7%)	30 (34.1%)
Related to KN046	0	6 (20.0%)	2 (4.4%)	1 (16.7%)	0	9 (10.2%)
Subjects with at least 1 IRR	0	7 (23.3%)	6 (13.3%)	2 (33.3%)	0	15 (17.0%)
Subjects with at least 1 irAE	0	20 (66.7%)	15 (33.3%)	5 (83.3%)	0	40 (45.5%)
Subjects with at least 1 CTCAE Grade ≥ 3 irAE	0	4 (13.3%)	0	0	0	4 (4.5%)
Subjects with at least 1 SAE during treatment 	1 (100%)	9 (30.0%)	4 (8.9%)	1 (16.7%)	4 (66.7%)	19 (21.6%)
Related to KN046 	0	4 (13.3%)	0	0	0	4 (4.5%)
Subjects with at least 1 TEAE Leading to Drug Withdrawn	0	2 (6.7%)	5 (11.1%)	1 (16.7%)	2 (33.3%)	10 (11.4%)
Related to KN046	0	2 (6.7%)	3 (6.7%)	0	0	5 (5.7%)

CTCAE version 5.0	1.0 mg/kg Q2W	3.0 mg/kg Q2W	5.0 mg/kg Q2W	5.0 mg/kg Q3W	300 mg Q3W	Total
	(N = 1)	(N = 30)	(N = 45)	(N = 6)	(N = 6)	(N = 88)
Subjects with at least 1 TEAE Leading to Death	1 (100%)	0	1 (2.2%)	0	3 (50.0%)	5 (5.7%)
Related to KN046	0	0	0	0	0	0

TEAE = treatment emergent adverse event; CTCAE = common terminology criteria for adverse event; IRR = infusion related adverse event; irAE = immune-related adverse event; SAE = serious adverse event.

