### **3. Study Design**

#### **3.1 Overall Design**

This is a Phase II, open-label, single-center, single arm study in subjects with advanced thymic carcinoma after failure of platinum-based combination chemotherapy. Subjects should have documented progressive disease after a platinum-based combination chemotherapy and an immune checkpoint inhibitor (PD-1 or PD-L1 antibodies). Subjects will be treated with KN046 at 5 mg/kg Q2W.

For individual subjects, the study begins with a screening period to assess eligibility up to and including 28 days prior to the first dose of KN046.

The treatment period begins on Day 1 of Cycle 1. All subjects will be treated with KN046 at 5 mg/kg Q2W intravenously until progressive disease according to RECIST 1.1, unacceptable toxicity, completion of 2 years of KN046 treatment, start of a new anti-cancer therapy, death, lost follow-up or withdrawal of informed consent, whichever comes first. After completion of 2 years of KN046 treatment, if investigator considers that subject continuing KN046 treatment will obtain clinical benefit, KN046 will be administered on a compassionate basis under the treating physician's responsibility. Treatment of KN046 beyond initial investigator evaluated progression (either clinical or imaging progression per RECIST 1.1 criteria) is allowed if the subject has an investigator assessed clinically stable status and is tolerating the treatment that meets the "Criteria for Continuation of Treatment Beyond Progression". Rechallenge with KN046 will be allowed if a patient responded and stopped the treatment for reasons other than progression while on treatment or toxicity.

Tumor evaluation will be performed at baseline, every 8 weeks in the first 12 months and every 12 weeks thereafter. Tumor evaluation will continue until confirmed progressive disease per RECIST 1.1, starting new anti-cancer therapy, withdrawal of informed consent, or subject's death, whichever comes first. Once objective response is observed, response should be confirmed by a second scan at approximately 8 weeks apart (no earlier than 4 weeks and no later than 8 weeks).

Clinical and laboratory assessments will be performed as described in Section 6.

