- 19 Tumor assessment will be performed using PET/CT at baseline, at time of best response, and when clinically indicated. CT scans of chest, abdomen and pelvis (Chest CT and MRI of Abdomen and Pelvis also acceptable) are also required at baseline, every 2 cycles (8 weeks) for the first year, then every 4 cycles (16 weeks) for the second year. Screening tumor assessment should be performed within 28 days of first trial treatment in order to document baseline status of tumor disease using RECIST 1.1 target and non-target lesions. During treatment period, the tumor assessment visit time window is  $\pm$ 7 days. CT or MRI scan (if MRI is used, CT of chest is mandatory) should always be used in the same modality as the screening period. If a tumor response is documented during the study, confirmation of the response should be performed according to RECIST 1.1, preferably at the regularly scheduled 8-week assessment interval, but no sooner than 4 weeks and no later than 8 weeks after the initial documentation of CR or PR. Confirmation of PR/CR can be done at an assessment later than the next assessment after the initial documentation of PR/CR. If disease progression is documented, confirmation of PD is required, preferably at 8-week assessment interval (but no sooner than 4 weeks and no later than 8 weeks). Tumor assessment will continue until confirmed disease progression per RECIST 1.1, start of new anti-cancer therapy, or withdrawal of informed consent, whichever comes first. If treatment discontinuation is due to reasons other than RECIST 1.1 defined progressive disease, tumor assessment should continue until RECIST 1.1 defined progressive disease, start of new anti-cancer therapy, or withdrawal of informed consent, whichever comes first;
- 20 Brain CT/MRI scan (either, with contrast preferred) is required at screening if not performed within the previous 42 days prior to first trial treatment. During treatment period, brain CT/MRI scan should be done if clinically indicated by development of new specific symptoms;
- 21 Each KN046 will be administered intravenously over at least 90 minutes (90-120 minutes). After the completion of KN046 infusion, subject should be observed at site for at least 2 hours.
- 22 If necessary to confirm postmenopausal status
- 23 Day 1 of each cycle only
- 24 To occur on Day 1 of odd Cycles only
- 25 If ANA or ENA positive, rheumatologic workup indicated.
- 26 Will only repeat ctDNA if genetic alteration detected at baseline.

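### PFS in section 10.3 has no death event, DOR in section 10.2 counts only cancer death, and neither has a censoring rule

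*Combined protocol and SAP*

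**What the plan says.** - **PFS.** Section 10.3 is a single sentence: "PFS is defined as the duration of time from start of treatment to time of progression". The Protocol Summary and section 12.4.2 list PFS as an endpoint but do not redefine it.
- **DOR.** Section 10.2 measures confirmed responders from first documented response "to the date of first documented disease progression or death due to underlying cancer". It also requires a listing by subject, with Kaplan-Meier curves where appropriate.
- **Analysis.** Section 12.4.2 makes DOR, PFS and OS secondary endpoints, estimated by Kaplan-Meier, with PFS and OS rates at, for example, 6 and 12 months. It names Clopper-Pearson limits for those rates. It gives no event definition and no censoring rule.
- **Scan schedule.** Footnote 19 to Table 4 says: "Tumor assessment will continue until confirmed disease progression per RECIST 1.1, start of new anti-cancer therapy, or withdrawal of informed consent, whichever comes first". Section 3.1 has a similar list that adds death. These rules say when imaging stops, not how the analysis treats a patient whose imaging has stopped.
- **Progression.** Section 10.1 makes site-assessed RECIST 1.1 the basis for disease status. Footnote 19 and section 7.2 ask for progression to be confirmed, within a window of 4 to 8 weeks.

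**The concern.** Read literally, a patient who dies before a scan shows progression has no PFS event. A responder who dies of toxicity has no DOR event. The usual programming consequence is censoring, and censoring a death makes the drug look better.

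This matters more in a single-arm, open-label, site-assessed trial, because no control arm carries the same bias. PFS will naturally be read beside the figures in the background sections: a median of 4.2 months for pembrolizumab in thymic carcinoma, and 2.69 months for KN046 after a prior checkpoint inhibitor. If those figures count deaths, the comparison is not like with like. With no censoring rule in place, choices about new therapy, withdrawal, missed scans and unprogressed deaths could be made after the data are seen.

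**Working it through.** **1. The plan's own figures.** The only design calculation is the Simon design (10 patients, stop at 0 responses; 29 patients, reject at 3 or fewer). The probability of early termination at 5% is 0.95^10 = 0.599. Expected N is 10 + 19 × (1 − 0.5987) = 17.62. The exact two-stage binomial sums give a type I error of 0.0468 and power of 0.8011. All agree with section 12.1, and none uses PFS or DOR.

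**2. The two definitions side by side.**

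| What happens to a responder | PFS (10.3) | DOR (10.2) |
|---|---|---|
| RECIST progression | Event; first or confirmatory scan not stated | Event at first documentation |
| Cancer death, no documented progression | Not an event | Event |
| Death from another cause, including toxicity | Not an event | Not an event |
| New therapy, withdrawal, missed scans | No rule | No rule |

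The second row is a direct disagreement between the two sections.

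**3. Size for PFS.** Let s be the share of first events that are deaths without documented progression. With constant hazards, the total hazard is h = ln 2 / median PFS. If those deaths are censored, Kaplan-Meier estimates exp(−h(1 − s)t), so the reported median is the true median divided by (1 − s). The documents do not give s, so the values below are assumptions. The starting medians are the two quoted in the background, used only as illustration.

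| s | Inflation of median | From 2.69 months | 6-month rate | From 4.2 months | 6-month rate |
|---|---|---|---|---|---|
| 0% | none | 2.69 | 21.3% | 4.20 | 37.1% |
| 5% | 1/0.95 = 1.05 | 2.83 | 23.0% | 4.42 | 39.0% |
| 10% | 1/0.90 = 1.11 | 2.99 | 24.9% | 4.67 | 41.0% |
| 20% | 1/0.80 = 1.25 | 3.36 | 29.0% | 5.25 | 45.3% |

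**4. What the phase I tables suggest about s.**
- Progressions as the reason for stopping at 5 mg/kg Q2W: 12 in Table 2-1 and 14 in Table 2-7, together 26. No stop at that dose is coded as death.
- The row "Subjects with TEAE Leading to Death" in the first Table 2-2 shows 2 of 30 at that dose. (Its title names KN046-CHN-001, but its N = 54 columns are those of KN046-AUS-001.) Table 2-8 shows 1 of 45. That makes 3 fatal events.
- Counting all 3 as first events gives 29/26 = 1.12, s = 3/29 = 10.3%, and 2.69 × 29/26 = 3.00 months. Whether these patients had already progressed is not stated.
- Stop reasons pooled over doses give 27/26 = 1.04 (KN046-AUS-001) and 39/36 = 1.08 (KN046-CHN-001).
- A footnote to Table 2-7 reads: "Other reasons including eight patients discontinued due to clinical deterioration". That is 8 of 9, so at least 4 of the 5 such patients at 5 mg/kg Q2W. If 4 or 5 of them died before a progression scan, a pessimistic assumption, the ratio is 30/26 = 1.15 or 31/26 = 1.19.

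**5. Size for DOR.** At the 20% target, 0.20 × 29 = 5.8, or about 6 responders. With the crude fatal-event rate of 3/75 = 4%, the chance that none has such a death is 0.96^6 = 0.78, and that exactly one has is 6 × 0.04 × 0.96^5 = 0.20. So 0 or 1 responder is affected with probability about 0.98. This is indicative only. Median therapy in those trials was 11 and 12 weeks, while responders here may be treated for 2 years. The cause of those deaths is not given, and a cancer death would already end DOR.

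**6. Dating of progression.** If the confirmatory scan set the date, a patient's PFS would lengthen by 4 to 8 weeks, that is 28 to 56 days or 0.92 to 1.84 months. Section 10.2 settles this for DOR; section 10.3 leaves it open.

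**The case against.** The strongest defence is that PFS conventionally includes death and that little depends on it here. Several parts of that stand. PFS and DOR are descriptive and carry no hypothesis. OS is a separate endpoint with survival contact every 12 weeks, so deaths will be reported. DOR is listed by subject, so an unusual death among about six responders would be visible. The pooled stop reasons suggest a shift of only 4% to 8%.

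The appeal to convention does not stand. Section 10.2 shows that death was considered and limited to cancer death, so a programmer following the text would leave other deaths out. An OS curve or a listing does not correct a PFS curve.

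Some stronger readings are tempting but unsupported:
- A reader might infer from section 3.1, which mentions "either clinical or imaging progression per RECIST 1.1 criteria", that clinical progression could count as a PFS event. That phrase belongs to the rule on treatment beyond progression, and section 10.1 makes RECIST 1.1 the measure. Only initial versus confirmed progression is open.
- A reader might take the stop reasons at 5 mg/kg Q2W (26 progressions, no deaths) as proof of no bias, or as the basis for a firm ceiling on it. Three fatal events are tabulated at that dose, so neither follows.
- No KN046-related death in 54 + 88 = 142 patients does not cap the DOR effect. It covers drug-related deaths only, over short exposure, while the gap is all non-cancer deaths.
- The Clopper-Pearson wording might look like a serious interval error. On one reading (Kaplan-Meier estimate with Clopper-Pearson limits on n = 29), simulated coverage was 93% to 97% with 5% to 40% drop-out by month 6. That is immaterial.

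**Conclusion.** The point holds on the text. What is called PFS is time to progression, DOR ignores non-cancer deaths, the two sections disagree on a responder's cancer death without documented progression, and no censoring rule exists.

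If the omitted deaths are censored, the bias is upward. Its size cannot be derived from the documents. Assumed shares of 5% to 20% inflate median PFS by about 5% to 25%, and the fatal events at this trial's dose point to about 12%. These figures rest on constant hazards and on phase I events in mixed tumours standing in for this population. For DOR, probably 0 or 1 responder is affected.

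A reader might infer that the trial's conclusion is at risk. It is not: response rate, N = 29, the stage 1 rule and the final rule do not use these endpoints. This is a definition to correct before analysis, not a design fault.

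**What to change.** - **10.3:** PFS runs from first dose to first documented RECIST 1.1 progression, dated at the first scan that shows it, or death from any cause, whichever is first.
- **10.2:** DOR ends at first documented RECIST 1.1 progression or death from any cause.
- **Both, censoring:** patients without an event are censored at the last adequate tumour assessment, or at the last one before new anti-cancer therapy if that comes first. For PFS, patients with no post-baseline scan and no death are censored at the start date. The text should define an adequate assessment and say how an event after missed scans is handled.
- **Sensitivity:** starting new therapy after clinical deterioration may be informative, so add one analysis counting clinical progression or new therapy as an event.
- **12.4.2 (minor):** take the 6- and 12-month PFS and OS rates and their intervals from the Kaplan-Meier curve, and keep Clopper-Pearson for the response rate.

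The cost is a few sentences and one extra analysis. Scans, survival status and new therapy are already collected, and no visit, patient number or decision rule changes. The one downside is that PFS and DOR may look slightly less favourable.
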